Before enrollment, physicians in charge must explain about this study with written and verbal explanation to all potential patients and/or their close relatives, using materials approved by institutional review board (IRB) in Nippon Medical School. Physicians guarantee potential patients and/or their close relatives chances to ask questions and sufficient time to decide whether they attend the study or not. Physicians in charge obtain informed consent from the potential patients after confirming their understanding and free will.

When new information about efficacy and safety of rt-PA or MT, that may affect the participants' attendance to this study, written materials must be revised after IRB approval, and re-consent is obtained from the patients or their close relatives.

Because the potential patients for this study have stroke, consent from their close relatives is permitted due to difficulty in obtaining consent because of disturbance of consciousness, aphasia, or weakness. When the consent is obtained from patients' relatives, the closest relative should be selected. Moreover, explanation to the patient must not be omitted even if the informed consent is obtained from relatives.

We have prepared the written explanation with easy expression so as potential patients and their relatives can understand.

10 Study design

[figure not shown]
11) The kind of the study and study design

The kind of the study: interventional

Study design: multicentre, randomized, open-label study

12) Outline of the study

To elucidate the efficacy of MT without rt-PA, compared with MT with rt-PA, randomized controlled study is conducted. Medical history taking and examinations are performed just before the informed consent and physicians ascertain the eligibility. When cessation of participation is applied from the patients or their relatives, patients are immediately removed from the study.

[MT without rt-PA group]

MT without rt-PA

Rt-PA therapy will be performed when MT is difficult to perform.

MT is regarded as difficult when time from groin puncture to guiding catheter placement exceeds 30 min.

[MT with rt-PA]

MT is performed after rt-PA therapy.

13) Rt-PA should be administered within 4.5 hours from symptom onset. The amount of 0.6mg/kg (maximum of 60 mg) is administered, 10% as bolus, and the rest of 90% as continuous infusion over one hour.

14) Concomitant treatment

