Below drugs must not concomitantly used within 24 hours after rt-PA therapy: warfarin, dabigatran, rivaroxaban, apixaban, and edoxaban.

15) Management and delivery of the drugs and the devices

The pharmaceutical and mechanical treatment performed in this study is approved as the treatment for stroke by the authority in Japan. Physicians use drugs or devices in the individual hospital.

16) Medication guidance

Not applicable

17) Case enrolment and random allocation

Physicians in charge should try to include all the patients who meet the inclusion criteria, and not to exclude from the study deliberately. Immediately after confirmation of LVO and obtaining consent from the patient, physicians allocated patients into specific group and avoiding treatment delay due to participation to this study.

The allocation is conducted with web-based system. After entering institutional ID and password, and completion of checklist, the system presents the results of allocation:

A) MT without rt-PA

B) MT with rt-PA

18) Patients eligibility

Physicians in charge must ascertain that the patients satisfy all the inclusion criteria and not correspond to none of the exclusion criteria (see p. 7-9).

19) Treatment after study participation

In this study, standard medical treatment is provided after hyperacute management, so standard medical treatment is continued to be provided for patients belonging to both groups.

20) Biological samples from study participants

In this study, biological sample from study participants is used only for study outcomes. All samples are discarded after anonymization. The storage period for case report forms ends the latter day of 5 years after announcement of study completion or 3 years after final result of the study is published.

11. Study outcome

Primary efficacy endpoint

- Favorable outcome defined as mRS score 0-2 at 90 days after stroke onset (non-inferior)(intention to treat analysis)

Secondary efficacy endpoints

- The mRS score at 90 days (shift analysis, non-inferior)

- Poor outcome defined as mRS score 5-6 at 90 days after stroke onset
- Poor outcome defined as mortality at 90 days after stroke onset
- Favorable outcome defined as mRS score 0-1 at 90 days after stroke onset
- Favorable outcome defined as mRS score 0-2 at 90 days after stroke onset
- Favorable outcome defined as mRS score 0-3 at 90 days after stroke onset
- Favorable outcome defined as mRS score 0-1 at 90 days after stroke onset (non-inferior)

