Adverse events: Any Intracerebral hemorrhage within 36 h and 7 days (± 1 day) after treatment, Symptomatic intracerebral hemorrhage (SITS-MOST criteria and NINDS criteria), and other hemorrhagic complications.

4) Vital signs and laboratory data

Blood pressure (on admission, before treatment), Heart rate, Body temperature

Laboratory data: (WBC, Hemoglobin, Platelet count, Glucose, HbA1c, BNP, PT-INR, aPTT)

Anticoagulant drugs, Antiplatelets, or Statins before admission

5) Follow-up

mRS 90 days (± 10 days) after onset (When mRS increase from pre-morbid mRS, denote whether the deterioration is due to stroke)

※the mRS was assessed by physical examination or telephone interview at 90 days after onset by a third independent observer, who was also blinded.

Etiology (TOAST criteria)

Symptomatic recurrence during admission

Surgical intervention

6) Other adverse events

Other adverse events are defined as all unfavorable events such as abnormal laboratory values and adverse reactions, regardless of causal relationship with drugs or treatments. Describe the details of adverse effects, timing of onset / recover, degree, treatment, outcome, severity assessment, and relevance with the study drug or treatment in the medical chart and case report form. Follow up if necessary. The severity of adverse events is defined as (1) mild: the state that study participation can be continued without treatment, (2) moderate: the state that study participation can be continued with treatment, and (3) severe: the state that study participation should be suspended.

13. Study discontinuation

3) Study discontinuation criteria for each participant

Study participants who meet the below situation will be excluded from this study.

- vi. Offer to decline participation or withdrawal of consent from the patient or their representatives.
- vii. Find out not to meet the inclusion criteria after study participation
- viii. The study terminates early
- ix. Difficult to study participation due to adverse events
- x. The participant should be excluded from the study for other reasons than the above, judged by the attending physician

When the participant is excluded from this study, the date, reason, or situation of discontinuation will be recorded on their medical chart and case report form. Appropriate examinations will be performed on discontinuation to evaluate the efficacy and safety.

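### Section 13 excludes randomised patients for later-found ineligibility, adverse events or the attending physician's judgement, and nothing keeps them in day-90 follow-up for the intention-to-treat primary analysis

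*Supplement*

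**What the plan says.** All references are to the final protocol.

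- **Section 11** labels the primary endpoint, mRS 0-2 at 90 days, as "non-inferior)(intention to treat analysis". It lists a per-protocol version among the secondary endpoints.
- **Section 15** describes the primary test as an unadjusted logistic regression with an odds-ratio margin of 0.74. It mentions secondary per-protocol analyses, but does not say who belongs to either population or how a missing mRS is handled.
- **Section 13**, criteria for each participant, opens with "Study participants who meet the below situation will be excluded from this study". Besides withdrawal (vi) and early termination of the study (viii), it lists:
  - later-found ineligibility, as criterion vii: "Find out not to meet the inclusion criteria after study participation"
  - adverse events, as criterion ix: "Difficult to study participation due to adverse events"
  - an open-ended ground, as criterion x: "The participant should be excluded from the study for other reasons than the above, judged by the attending physician"
- **Section 13** then provides: "Appropriate examinations will be performed on discontinuation to evaluate the efficacy and safety". It treats exclusion before treatment as a separate case, so exclusion after treatment is foreseen.
- **Section 12, item 6** grades adverse events, with the top grade defined as "severe: the state that study participation should be suspended".
- **Section 10** describes the trial as open label. **Section 12, item 5** gives the day-90 mRS to a blinded independent observer, in person or by telephone.

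**The concern.** An intention-to-treat analysis of a day-90 score needs that score for every randomised patient. Section 13 speaks of leaving the study, not of stopping a procedure, and it gives no route by which a patient excluded under vii, ix or x still reaches the day-90 assessment.

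These losses are unlikely to be random. The top adverse-event grade is itself defined by suspension of participation. Section 14 counts death and disability among severe adverse events, and these are close to what the mRS measures. Criterion x is open-ended and lies with a physician who knows the allocation. Blinding the observer does not help a patient whose score is never taken.

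At stake is the noninferiority conclusion. Losing non-favourable patients mainly from the direct arm pushes the odds ratio up, towards noninferiority. Losing them mainly from the bridging arm, for example after haemorrhage, pushes it down and can hide a true result.

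**Working it through.** **1. The passages side by side.** Section 11 requires the randomised set. Section 13 takes some of that set out of the study. Three texts could reconcile them: a definition of intention to treat, a statement that excluded patients are followed to day 90, or a rule for a missing mRS. None of the three is present.

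**2. The plan's own sample size.** Inputs from Section 6: 48.6% favourable with direct thrombectomy, 35.2% with bridging, 89 per group, 10% dropout. From Section 15: margin 0.74, one-sided 97.5% confidence. Power is not stated, so 80% is assumed.

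- Assumed odds ratio: (0.486/0.514)/(0.352/0.648) = 1.741.
- n per group = [1/(0.486×0.514) + 1/(0.352×0.648)] × (1.960 + 0.842)² / (ln 1.741 − ln 0.74)² = (4.003 + 4.384) × 7.849 / 0.8553² = 89.98.
- Dropout: 178/0.9 = 197.8, so 198.

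This agrees with the stated 89 per group (90 here) and 200 in total. No sample-size figure is at fault on this point.

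**3. Removals from the direct arm only (worst case).** Assume 100 per arm, with 40 favourable in the direct arm and 35 in bridging; 35 is close to the planned 35.2%, and 40 is an assumption. The lower bound is exp(ln OR − 1.96×SE), where SE² is the sum of the reciprocals of the four cells.

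- None removed: OR = (40/60)/(35/65) = 1.238. SE² = 1/40 + 1/60 + 1/35 + 1/65 = 0.0856, SE = 0.2926. Lower bound 0.698, so noninferiority is not shown.
- Five non-favourable removed: OR = (40/55)/(35/65) = 1.351. SE² = 1/40 + 1/55 + 1/35 + 1/65 = 0.0871, SE = 0.2952. Lower bound 0.757, so noninferiority is shown.

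Four removals already give 0.745; three give 0.732.

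**4. The other direction.** With 43/100 against 35/100, OR = (43/57)/(35/65) = 1.401 and the lower bound is 0.792. Removing 5 non-favourable bridging patients gives OR = (43/57)/(35/60) = 1.293 and a lower bound of 0.728, so noninferiority is lost.

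**5. Balanced removals.** With 40/95 against 35/95, OR = (40/55)/(35/60) = 1.247 and the lower bound is 0.696, almost the same as 0.698. The harm comes from imbalance.

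**6. Where it matters.** With 49/100 against 35/100, near the planned rates, the lower bound is 1.011 and noninferiority holds with or without removals from the direct arm. With 35/100 in both arms, five direct-arm removals move it only from 0.559 to 0.603. The conclusion is fragile for results between these.

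**7. Error rate.** Assume bridging at 35.2%, a true odds ratio equal to the margin (direct arm 28.7%), 100 per arm, and removals of non-favourable patients from the direct arm only. Exact binomial enumeration gives a false noninferiority rate of 2.4% with none removed, 3.4% with 2, 4.6% with 5 and 7.4% with 10.

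**The case against.** The strongest reply is that Section 13 governs participation and Section 11 governs analysis. Read together, a discontinued patient leaves the per-protocol set and stays in the intention-to-treat set. Section 12 sets the day-90 mRS without an exception for discontinued patients. Mortality, mRS 5-6 and symptomatic haemorrhage are endpoints that would lose their content if such patients were dropped. Each exclusion must be recorded with its date and reason.

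Much of this stands, and it limits what may be concluded:

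- A reader might infer that Section 13 deletes these patients' data or flatly contradicts intention to treat. It does not say so. Nor does it say that the examination on discontinuation is the last one.
- A reader might infer that every severe adverse event leads to exclusion. Criterion ix is narrower: participation must have become difficult.
- A reader might infer that physicians would use criterion x to discard bad outcomes. The text gives the opportunity; nothing shows intent or occurrence.
- The sentence in Section 10 on removing patients from the study might look like further support. It applies only when the patient or relatives ask to stop.
- Five losses, all non-favourable and all from one arm, is a worst case. The 10% dropout in Section 6 is a general allowance over both arms. If haemorrhage drove exclusion and omitting rt-PA reduces haemorrhage, as the protocol supposes, losses would fall more on bridging and work against noninferiority.

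What does not stand is that the intention-to-treat label settles the matter. A site that follows Section 13 literally may stop following the patient, and a label cannot supply a score that was never collected.

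**Conclusion.** The point holds as a defect in a stated rule, not as proof of a biased analysis. Followed as written, Section 13 can end follow-up for reasons tied to outcome, partly at the discretion of an unblinded physician, and the plan has no text that protects the primary analysis. The direction of any bias cannot be predicted.

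As to size, four or five one-sided losses are enough to change the conclusion when the result lies near the margin. This rests on 100 per arm, the assumed counts, and every loss being non-favourable and from one arm. Near the planned effect, direct-arm losses would not change the conclusion, and balanced losses would do little. Since the primary conclusion is exposed and the repair is cheap, it should be made before the data are analysed.

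**What to change.** 1. Reword Section 13 so that criteria vii, ix and x end study procedures only, not follow-up or analysis.
2. Define intention to treat in Sections 11 and 15 as all randomised patients, analysed in their allocated arm.
3. Collect the day-90 mRS for all of them, except those who withdraw consent or decline further participation (criterion vi). The telephone interview already allowed in Section 12 is sufficient.
4. Define the per-protocol set, and let exclusions for eligibility or protocol deviation apply only there.
5. State in Section 15 a rule for a missing mRS, with a sensitivity analysis that is conservative for noninferiority, for example counting missing direct-arm outcomes as not favourable. Multiple imputation by arm is one acceptable main rule among several.

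Section 10 needs no change on this point. The cost is protocol wording and a few extra telephone assessments; no patients are added.

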Under the current guidelines, MT should be conducted in conjunction with rt-PA, when patients have indications for rt-PA. Therefore, there is no RCTs investigating the effectiveness of MT without rt-PA. One retrospective study revealed that MT without rt-PA, compared with MT plus rt-PA, reduced hemorrhagic complications and mortality.¹⁰

To skip rt-PA can reduce hemorrhagic complications and achieve better outcome. Therefore, we conduct prospective, multicentre RCT to elucidate the efficacy of MT without rt-PA for hyperacute ischemic stroke patients with LVO.

3. Purpose of the study

The aims of the present study is to elucidate the difference in clinical outcome, hemorrhagic complications, onset-to-reperfusion time, and the rate of effective recanalization between MT with and without rt-PA in acute stroke patients with LVO.

4. Study period

From November 1st, 2016 through October 30th, 2019 (study entry ends July 31st, 2019).

5. Study site

Department of Neurology, Nippon Medical School hospital

6. Sample size

Favorable outcome (modified Rankin scale [mRS] 0-2, 3 months after stroke onset) was assumed to be 48.6% in the MT without rt-PA group and 35.2% in the MT with rt-PA group,¹¹ the required number of patients is calculated to be 89 patients in each group, for a total of 178 patients. Assuming a dropout rate of 10%, 200 patients (100 patients in each group) has been set.

7. Drugs and devices used in the study

3) Information about drugs and devices

Drug: alteplase (Activacin® [Kyowa Hakko Kirin] and Grtpa® [Tanabe Mitsubishi Pharmacy])

Devices: Devices used for revascularization, such as: Penumbra® (Medico's Hirata), Trevo® (Stryker), Solitaire® (Medtronic), Revive® (Johnson & Johnson), Gateway® PTA Catheter, Wangspan® stent, Precice®, Carotid Wall® stent, and PROTÉGÉ®.

4) Expected adverse effect of the drugs or malfunction of the devices

Hemorrhagic complications are known as adverse effects of these drugs and devices.

When severe hemorrhagic complication occurs, every treatment is based on taking the highest priority on participants' safety.

8. Patient population

4) Patient condition

Ischemic stroke

5) Inclusion criteria

 Inclusion criteria

1. Age ≥ 18 and < 86 years at the time of informed consent
 2. Clinical diagnosis of acute ischemic stroke with clinical symptoms
 3. Modified Rankin scale score ≤ 2
 4. ICA or M1 occlusion on MRA or CTA
 5. Initial NIHSS ≥ 6
 6. ASPECTS on initial DWI ≥ 5 or on initial CT ≥ 6

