15. Statistical Analysis Plan

The primary study outcome measure was noninferiority of the favorable outcome at 90 days. We first used unadjusted logistic regression to test whether direct MT therapy was noninferior to bridging therapy. To satisfy the noninferiority hypothesis, the lower bound of the one-sided 97.5% confidence interval for the odds ratio (OR) of the primary outcome of the Direct MT group compared with the Bridging group needed to exceed 0.74. This noninferiority margin was derived from a previous meta-analysis of bridging therapy compared with the best medical treatment,¹² with the margin defined according to the upper bound of the 95% confidence interval for the OR of the primary outcome with standard medical care versus the combination of medical care and MT. The margin of 0.74 represents the midpoint between the upper bound of the 95% confidence interval of the estimated effect of the standard medical care and 1.0 (using bridging therapy with medical care and MT as a reference). The secondary efficacy analyses included the comparison of ordinal scores on the modified Rankin scale to test for the noninferiority of the direct MT vs bridging therapy with ordinal logistic regression (shift analysis), where the OR is calculated for each cut-point across the mRS (for example, 0 versus 1–6, then 0–1 versus 2–6, and so on), and then a summary OR is calculated from the individual ORs, under the assumption that the individual ORs are the same. We also performed secondary analyses of the primary outcome with adjustment for minimization and key prognostic covariates, as well as secondary analyses in the per-protocol population. Next, clinical characteristics, recanalization success rate, hemorrhagic event rate (Any ICH, symptomatic ICH and other hemorrhagic complication), mortality and other MT parameters were compared between the two groups. For ease of interpretation, all reported P-values for noninferiority are multiplied by 2, so that an alpha of 0.05 can be used in analyses. The other P-values are two-sided. All P-values were pre-specified not to be adjusted. JMP version 11 software (SAS Institute, Cary, NC) was used for the analysis.

16. Privacy policy

- 1) When treating raw data or consent forms, consider participants' privacy.
- 2) Identifying code is used in forms submitted to outside hospital, instead of names.

- 3) Correspondence table between participants' name and identifying code is strictly kept in the department of neurology.

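### The deciding non-inferiority test is unadjusted, so it is valid but less precise than the planned baseline data allow; a covariate-standardised marginal odds ratio would narrow the limit compared with 0.74

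*Supplement*

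**What the plan says.** Section 15 (Statistical Analysis Plan) of the final protocol states the primary test: "We first used unadjusted logistic regression to test whether direct MT therapy was noninferior to bridging therapy". The criterion is that "the lower bound of the one-sided 97.5% confidence interval for the odds ratio (OR) of the primary outcome", for direct MT "compared with the Bridging group needed to exceed 0.74". The same section lists "secondary analyses of the primary outcome with adjustment for minimization and key prognostic covariates". It names neither the minimization factors nor the covariates, and it does not say whether the adjusted odds ratio is conditional or marginal.

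That phrase is the only sign of minimization. The item on case enrolment and random allocation in Section 10 describes a web-based system and gives no method or factors.

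Section 12 collects age, admission NIHSS, pre-treatment ASPECTS (on CT or on DWI), occluded vessel and premorbid mRS.

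Section 6 gives the design assumptions. Favorable outcome (mRS 0–2) "was assumed to be 48.6% in the MT without rt-PA group and 35.2% in the MT with rt-PA group", and "the required number of patients is calculated to be 89 patients in each group, for a total of 178 patients". It continues: "Assuming a dropout rate of 10%, 200 patients (100 patients in each group) has been set".

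**The concern.** The trial stands or falls on one confidence limit from about 178 evaluable patients, so avoidable width in that limit matters. Two features of the plan suggest that some of the width is avoidable.

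- Minimization makes the arms more alike on its factors than simple randomisation would. The model-based standard error of an unadjusted odds ratio takes no account of this, so it overstates the true sampling variation if those factors are prognostic.
- Baseline measures that the plan itself treats as key prognostic covariates play no part in the deciding test.

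The type of adjustment is critical. Putting covariates into the logistic regression changes the target to a conditional odds ratio, whose standard error is larger. Standardising the fitted risks over all randomised patients keeps the marginal odds ratio, which is the quantity the unadjusted model estimates, and reduces its standard error.

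**Working it through.** **Inputs.** From Section 6: 48.6% (direct MT) and 35.2% (bridging), 89 per arm. From Section 15: margin 0.74, one-sided 97.5% limit (z = 1.960). Power is not stated; 80% is inferred because it reproduces the sample size. Prognostic strength is not in the documents; I assume a baseline risk score with SD 0.8, 1.1 or 1.5 on the log-odds scale.

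**Reproducing the plan's figure.**
- OR = (0.486/0.514)/(0.352/0.648) = 1.741; ln(1.741/0.74) = 0.855.
- Variance term: 1/(0.486×0.514) + 1/(0.352×0.648) = 4.003 + 4.384 = 8.387.
- n per arm = 8.387 × (1.960 + 0.842)² / 0.855² = 89.98, that is 90 against the stated 89.

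**Unadjusted test with 89 per arm.**
- Planned rates: SE = √(8.387/89) = 0.307. Power = Φ(0.855/0.307 − 1.96) = 79.6%.
- Equal rates (41.9% in both arms, the mean of the two planned rates): SE = √(2/(0.419×0.581)/89) = 0.304. An observed OR of 1 has lower limit exp(−1.96×0.304) = 0.55. Pass rate = Φ(0.301/0.304 − 1.96) = 16.6%.

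**Standardised marginal OR.** The SEs come from simulation with 89 per arm, 3,000 runs per scenario, three fitted covariates, an influence-function SE and simple 1:1 allocation. The unadjusted SE in the same runs was 0.309 at the planned rates. Power is Φ(0.855/SE − 1.96). For equal rates, I scale 0.304 by the ratio of each SE to 0.309. The last column is 1 − (SE/0.309)².

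| Assumed SD | SE at planned rates | Power, formula (simulated) | Pass rate at equal rates, formula (simulated) | Patients saved for the same precision |
|---|---|---|---|---|
| 0.8 | 0.291 | 84% (84%) | 18% (18%) | 11% |
| 1.1 | 0.279 | 87% (89%) | 19% (19%) | 18% |
| 1.5 | 0.262 | 90% (92%) | 21% (21%) | 28% |

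The unadjusted analysis in these runs had 79–81% power at the planned rates and a pass rate of about 16% at equal rates. Separate sets of runs agree within simulation error; across all of them the standardised analysis gives about 84–91% and 18–22%.

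**Conditional OR from adjusted logistic regression.** In the same runs its SE at the planned rates was 0.34–0.38. Its pass rate at equal rates was 12.5–14.5%, below the unadjusted 16%. Any power gain at the planned rates comes from the conditional estimate lying further from 1, which does not happen when the true OR is 1.

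**Effect of balanced allocation.** The factors are unnamed, so I used allocation balanced on the risk score as an idealised stand-in for minimization. The unadjusted model SE stayed at 0.309 while its true sampling SD was 0.295, 0.278 and 0.263. The approximate rejection rate at a true OR of 0.74 is 1 − Φ(1.96 × 0.309/SD) = 2.0%, 1.5% and 1.1%, against 2.5% nominal. Simulation gave 2.1%, 1.9% and 0.9%.

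**Type I error of the standardised test.** With 6–9 covariates and no small-sample correction, 6,000 runs at a marginal OR of 0.74 gave a mean SE about 3–7% below the true sampling SD. The rejection rate was 2.5–3.05%; the unadjusted test gave 1.8–2.4%.

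**The case against.** The strongest reply is that nothing is wrong with the plan's test. It is pre-specified, its estimand is clear, and its type I error is at or below nominal. In a non-inferiority trial, conservatism guards against a false claim. An adjusted analysis is already planned, and the dispute is only over which analysis decides. The gain is smallest where it would matter most: with truly equal arms, about four in five trials would still fail. The prognostic strength is assumed. Minimization rests on one phrase with no factors named. The better precision is also not free, since an uncorrected robust SE with several covariates is somewhat too small.

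Most of this stands. A reader might infer that the unadjusted test is biased or inflates type I error; the text and the calculations show the opposite. A reader might also infer that promoting the planned adjusted logistic regression would narrow the interval; it would widen it and change the estimand. Nor can the documents establish how the allocation worked or how much it balanced prognosis.

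What the reply does not remove is the precision gain from covariates, which appears under simple 1:1 allocation too and so does not depend on minimization. The standardised analysis targets the same marginal OR and needs no new data.

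**Conclusion.** The point holds as one of efficiency. The deciding analysis is valid but less precise than the collected data allow, and it is conservative to the extent that minimization balances prognosis. For an assumed log-odds SD of 0.8–1.5, standardisation cuts the SE from about 0.31 to 0.29–0.26. It lifts power at the planned rates from about 80% to 84–91%, and the pass rate at equal rates from about 16% to 18–22%. It does not rescue the trial if the arms are equal.

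The direction of the effect is secure. Its size depends on the assumed prognostic strength, and the conservatism figures depend on an idealised balanced allocation. One further point is open: the documents do not say whether the meta-analysis odds ratio behind 0.74 was adjusted. The proposal keeps the plan's own marginal estimand, so it adds no new mismatch, but the sponsor should confirm that the margin suits it. The change is worth making; the existing test would not be invalid without it.

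**What to change.** In Section 15, make the primary analysis a standardised marginal odds ratio (g-computation).

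- Fit a logistic model with treatment, the minimization factors and a short fixed set of covariates: age, admission NIHSS, and ASPECTS with an indicator for CT or DWI.
- Average the predicted risks over all randomised patients under each arm and form the odds ratio from the two averages.
- Compare its one-sided 97.5% lower limit, from a small-sample-corrected robust SE or a bootstrap, with 0.74.
- List the minimization factors in the SAP and state the allocation method in Section 10.
- Keep the unadjusted odds ratio as a sensitivity analysis. If the conditional odds ratio is reported, do not test it against 0.74.

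The cost is revised SAP wording and a short script, possibly outside JMP 11, the software named in Section 15. No new data are needed. The statistical downside is type I error of up to about 3% against 2.5% if the small-sample correction is left out.
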